Appendix 2. Data Derivation Details

Appendix 2.1. Definition and Use of Analysis Windows in Reporting

Analysis windows will be used for PROs and vital signs, and laboratory tests.

If more than one observation from the same participant falls into the same analysis window, the value closest to the targeted day will be used as the observation for that visit. If two observations are equally close to the targeted day, the later will be used. All observations will, however, be included in the listings.

Table 3. Analysis Windows for PGIS and PGIC

Visit Label	Targeted Day	Analysis window for data sets
Baseline (Screening up to first dosing date)	Day 1	Last observation up to and including first dosing date
Day 15	Day 15	Day 8 – Day 21
Week 4	Day 28	Day 22 – Day 56
Week 12	Day 84	Day 57 – Day 126
Week 24	Day 168	Day 127 – Day 210
Week 36	Day 252	Day 211 – Day 308
Week 52	Day 365	Day 309 – end of study

Table 4. Analysis Windows for Vital Signs

Visit Label	Targeted Day	Analysis window for data sets
Baseline (Screening up to first dosing date)	Day 1	Last observation up to and including first dosing date
Day 4	Day 4 pre-dosing	Day 2 - Day 4 pre-dosing
Day 7	Day 7 pre-dosing	Day 5 - Day 7 pre-dosing
Day 15	Day 15 pre-GC	Day 8 - Day 15 pre-GC
Day 28	Day 28 pre-GC	Day 16 – Day 28 pre-GC
Week 12	Day 84 pre-GC	Day 29 – Week 12 pre-GC
Week 24	Day 168 pre-GC	Week 12 GC +1 day – Week 24 pre-GC
Week 36	Day 252 pre-GC	Week 24 GC +1 day – Week 36 pre-GC
Week 52	Day 364	Week 36 GC +1 day – end of study

Table 5. Analysis Windows for Laboratory Tests

Visit Label	Targeted Day	Analysis window for data sets
Baseline (Screening up to first dosing date)	Day 1	Last observation up to and including first dosing date
Day 4	Day 4 pre-dosing	Day 2 - Day 4 pre-dosing

Table 5. Analysis Windows for Laboratory Tests

Visit Label	Targeted Day	Analysis window for data sets
Day 7	Day 7 pre-dosing	Day 5 - Day 7 pre-dosing
Day 15	Day 15 pre-GC	Day 8 - Day 15 pre-GC
Week 12	Day 84 pre-GC	Day 16 – Week 12 pre-GC
Week 24	Day 168 pre-GC	Week 12 GC + 1 day – Week 24 pre-GC
Week 36	Day 252 pre-GC	Week 24 GC + 1 day – Week 36 pre-GC
Week 52	Day 364	Week 36 GC + 1 day – end of study

Table 6. Analysis for Immunogenicity

Visit Label	Targeted Day	Analysis window for data sets
Baseline (Screening up to first dosing)	Day 1 pre-dosing	Last observation prior to first dosing date
Day 7	Day 7 pre-dosing	Day 2 - Day 7 pre-dosing
Week 4	Day 28	Day 8 – Day 56
Week 12	Day 84	Day 57 – Day 126
Week 24	Day 168	Day 127 – Day 210
Week 36	Day 252 pre-GC	Day 211 – Day 308
Week 52	Day 364	Day 309 – end of study

Table 7. Analysis for IL-2 and CDS (GC day at each time point)

Visit Label	Targeted Day	Analysis window for data sets
Day 15	Day 15	Day 14 -Day 16
Week 12	Day 84	Day 70 - Day 98
Week 24	Day 168	Day 154 – Day 182
Week 36	Day 252	Day 238 – Day 266

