8.3.2. Vital Signs

Any untoward vital sign findings that are identified during the active collection period and meet the definition of an AE or SAE ([Appendix 3](#)) must be reported according to the processes in [Sections 8.4.1](#) to [8.4.3](#).

Vital signs will be monitored during and after study intervention infusions to assess for IRR (see [Appendix 9](#)). Vital signs will be taken before collection of laboratory tests. Height and weight will also be measured and recorded at screening only and captured on the CRF.

BP and PR assessment consists of a single measure of BP and a single PR. Sitting BP and PR measurement will be assessed with a completely automated device.

Manual techniques will be used only if an automated device is not available. BP and PR measurement should be preceded by at least 5 minutes of rest with the participant in a sitting position, in a quiet setting without distractions.

In amendment 3, Part C orthostatic vital signs including SBP, DBP, and PR will be collected as follows:

- Approximately 5 minutes pre-dose;
- Approximately 45 minutes, 2 hours, and then, every 2 hours until discharge, post dose.

Additionally, if a participant experiences treatment-emergent clinically significant orthostatic hypotension or syncope, then, in addition to supportive care, orthostatic vital signs including

DBP, SBP, and PR will be collected every 2 hours, until discharge. **Note:** if planned assessments (pre-dose and 45 min, 2 hr and 4 hour post-dose) overlap unplanned assessments, orthostatic vital signs will be measured only once, not twice at that time.

Measurement of orthostatic vital signs (SBP, DBP, and PR) will occur after:

1. participant has rested in supine position for 5 minutes
2. participant is in standing position for 1 min
3. Participant is in standing position for 3 minutes

Note: Clinically significant orthostatic hypotension (OH) is defined by a fall in systolic blood pressure over 20 mmHg or a fall of in diastolic pressure over 10 mm Hg within 3 minutes of standing. An increase in heart rate of over 30 bpm suggests postural tachycardia syndrome.(Freeman et al, 2011) In case of above, a Grade 3 AE will be documented.

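### Part C SAP Table 4 sets no pre-dose limit on the vital-sign baseline, and its Day 28 window sends on-time Day 29 to 31 visits to Week 12

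*SAP*

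**What the plan says.** SAP Part C section 6.6.3 summarises vital signs and their change from baseline. The windows are in Appendix 2.1, Table 4.

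- Baseline row: "Last observation up to and including first dosing date". The Day 4 row, by contrast, reads "Day 2 - Day 4 pre-dosing", and the Day 7 row stops at the dose in the same way.
- Day 28 row: "Day 16 – Day 28 pre-GC". Week 12 row: "Day 29 – Week 12 pre-GC".
- With several readings in one window, "the value closest to the targeted day will be used as the observation for that visit". Ties go to the later reading.

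On what is measured, Protocol 8.3.2 states: "Vital signs will be monitored during and after study intervention infusions to assess for IRR". For visit readings it states: "Sitting BP and PR measurement will be assessed with a completely automated device". Part C also takes orthostatic sets on each dosing day, before the dose and at about 45 minutes, 2 hours and 4 hours after it. These start once the "participant has rested in supine position for 5 minutes" and continue standing. They have their own row in the Part C Schedule of Activities (Protocol 1.3.3), but SAP Part C section 3.5.3 describes them under its Vital Signs heading.

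The schedule places GCs on Day 15 and at Weeks 12, 24 and 36. Day 28 is a safety follow-up visit with a window of ±3 days.

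**The concern.** Two rows of Table 4 give the wrong by-visit result if programmed as written.

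**Baseline.** The rule works on the calendar date, so a reading taken during or after the first infusion qualifies and, being later, replaces the pre-dose one. Change from baseline would then start from a value that may already carry a drug or infusion effect. If orthostatic sets are in the same data, baseline could even be a standing value set against later sitting values.

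**Day 28.** The window closes at an event that does not take place that day, and it cuts the permitted visit window. An on-time visit on Day 29, 30 or 31 is labelled Week 12.

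Safety is a secondary objective of Part C, and Protocol 4.2 says the extra vital-sign collection was added to learn more about events soon after dosing. A baseline that may itself be post-dose works against that aim.

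**Working it through.** The plan gives no figure of its own to reproduce here. The check applies the rules of Table 4 to the visit schedule.

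**1. Baseline rule on Day 1 (Part C)**

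Planned orthostatic times on Day 1 are pre-dose, 45 min, 2 h and 4 h (Protocol 8.3.2).

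- Rule as written, last reading on or before the dosing date: the 4 h reading.
- Rule with a pre-dose limit: the reading about 5 minutes before the dose.

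Write the selected baseline as Y_base = Y_predose + d, where d is the post-dose shift. Then

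reported change = Y_later − Y_base = (Y_later − Y_predose) − d.

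Every later change is off by d. The documents do not give d, and it may be near zero at 4 h.

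How many participants are affected depends on what Table 4 covers, which the SAP does not say:

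- Sitting readings only: each participant with an infusion-monitoring reading on Day 1 in the vital-sign data. That number is not given.
- Orthostatic sets as well: every participant with the planned Day 1 sets, 3 of them post-dose. On Days 4 and 7, 2 × 3 = 6 post-dose sets per participant would fall in no window, because those rows stop at the dose and the next rows start a day later.

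Table 5 (laboratory tests) has the same baseline wording. Protocol Appendix 2 has laboratory samples taken before infusion, so Table 5 is exposed only if an event-driven sample (Protocol 8.3.4) is drawn after the Day 1 dose.

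**2. Day 28 visit**

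Permitted days: 28 ± 3 = Days 25 to 31, which is 7 days. Week 12 target: Day 84.

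| Visit day | Table 4 window | Days from 28 | Days from 84 |
|---|---|---|---|
| 25 | Day 28 | 3 | 59 |
| 26 | Day 28 | 2 | 58 |
| 27 | Day 28 | 1 | 57 |
| 28 | Day 28 | 0 | 56 |
| 29 | Week 12 | 1 | 55 |
| 30 | Week 12 | 2 | 54 |
| 31 | Week 12 | 3 | 53 |

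So 3 of 7 permitted days are misassigned. An on-time Week 12 visit (Day 84 ± 5) is at most 5 days from target. It beats a reading 53 to 55 days away, and the Day 28 reading drops out of the by-visit summary. If there is no closer Week 12 reading, the Day 28 reading is reported as Week 12. If a participant has no Week 12 GC, which Protocol 7.1 requires for those who withdraw from treatment before three full doses, the end of that window is undefined.

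**3. How many Day 28 visits**

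The share of visits on Days 29 to 31 is not given. With assumed shares and 104 planned participants:

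- 10%: 0.10 × 104 = 10.4, about 10
- 25%: 0.25 × 104 = 26
- 3/7 (visits spread evenly over the window): 0.429 × 104 = 44.6, about 45

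**4. The same visit in the other Part C tables**

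For a visit on Day 30, Table 3 (Days 22 to 56) labels PGIS and PGIC as Week 4, Table 6 (Days 8 to 56) labels ADA as Week 4, and Table 4 labels vital signs as Week 12.

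**5. Other parts**

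Table 4 in the Part B SAP has the same two rows. Table 4 in the Part A SAP has only the baseline wording; its Day 28 window runs to end of study.

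**The case against.** The case on the other side is strongest against the baseline half. Protocol 8.3.2 calls for a single sitting measure, taken before laboratory samples, and laboratory samples precede the infusion. The scheduled Day 1 reading is therefore pre-dose by procedure, and if it is the only Day 1 reading in the data, the rule picks the right one. The documents do not say that infusion-monitoring readings are entered as vital-sign data, or that orthostatic sets are pooled with sitting readings. The sponsor's reporting standards, cited in SAP section 6.6.3, may supply a pre-dose baseline. The SAP also uses different windows for different data types on purpose, so a difference between tables is not an error in itself. Finally, all of this concerns descriptive output.

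Most of that limits the size of the problem. The baseline error is conditional on a post-dose Day 1 reading being in the data. But SAP section 3.5.3 lists the orthostatic readings under Vital Signs, no other vital-sign baseline is defined, and the sponsor's standards are not in the documents. The Day 4 and Day 7 rows show that a pre-dose limit was considered elsewhere in the same table. For Day 28, the fault is not that Table 4 differs from Tables 3 and 6. It is that its boundary cuts through the visit window the protocol allows, and nothing in the objection answers that.

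**Conclusion.** Both points hold and should be fixed. The Day 28 fault is certain on the text: 3 of 7 permitted days go to Week 12. The number of visits affected rests on an assumed share and on planned rather than attended visits; the range of about 10 to 45 of 104 is illustrative, not an estimate. The baseline fault is certain as a reading of the rule. Its effect depends on which Day 1 readings are in the vital-sign data and on a post-dose shift that is not given.

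The consequences are confined to descriptive safety summaries. The primary IL-2 analysis uses the windows of Table 7, all readings stay in the listings, and orthostatic hypotension is judged within a set and recorded as an adverse event, so it does not depend on this baseline.

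**What to change.** - **Baseline, Tables 4 and 5 (Part A: Table 4).** Define it as the last non-missing value before the start of the first infusion, of the same measurement type: sitting, or orthostatic by position.
- **Day 28, Table 4 in Parts B and C.** Remove the reference to a GC, extend the window past Day 31, and start Week 12 the day after it ends. Any end from Day 31 onward covers the permitted visits; Day 56 would match Table 3. Removing the GC reference alone is not enough, because Week 12 would still open on Day 29.
- **Minor.** State whether Table 4 covers the orthostatic sets. If it does, summarise dosing-day values by nominal time as change from the pre-dose value.
- **Minor.** In Part C Table 6, the ADA baseline targets the Day 1 pre-dose sample, but its window ends before the dosing date and so leaves that sample out. Align the two.

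The cost is edits to SAP tables and the matching programming. No new data are needed.

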3.5.3. Vital Signs

Vital signs will be assessed at Screening, Days 1, 4, 7, 15, 28, Weeks 12, 24, 36, 52, or ET visit. On dosing days, orthostatic vital signs including SBP, DBP, and PR will be collected approximately 5 minutes pre-dose, and approximately 45 minutes, 2 hours, and then, every 2 hours until discharge, post dose.

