6.6.3. Vital Signs

Vital signs and change from baseline and clinical significant change will be summarized according to Sponsor's standards.

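### SAP Part C Table 4 puts no pre-dose limit on the vital-sign baseline, so a Day 1 post-dose orthostatic set becomes baseline and no post-dose set is summarised as a post-dose result

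*SAP*

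**What the plan says.** SAP Part C 3.5.3, headed Vital Signs, covers the routine visit readings and then adds the dosing-day series: "On dosing days, orthostatic vital signs including SBP, DBP, and PR will be collected approximately 5 minutes pre-dose". It continues with readings at about 45 minutes, 2 hours and every 2 hours until discharge. Protocol 8.3.2 names the planned post-dose times as 45 minutes, 2 hours and 4 hours, each with a supine reading and standing readings at 1 and 3 minutes. The Part C schedule (protocol 1.3.3) places the series on Days 1, 4 and 7.

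Appendix 2.1 of the Part C SAP applies analysis windows to vital signs and keeps one value per window. In Table 4:

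- The baseline row has target Day 1 and the rule "Last observation up to and including first dosing date".
- The Day 4 window is "Day 2 - Day 4 pre-dosing".
- The Day 7 window is "Day 5 - Day 7 pre-dosing".
- The next window opens on Day 8.
- For ties within a window: "If two observations are equally close to the targeted day, the later will be used".

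On reporting, 6.6.3 states: "Vital signs and change from baseline and clinical significant change will be summarized", following sponsor standards that are not part of the documents. No post-dose timepoint appears in Table 4 or in 6.6.3.

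**The concern.** A baseline should describe the participant before treatment. The Table 4 rule is bounded by calendar date, and on the first dosing date most of the scheduled orthostatic readings are taken after the infusion. A rule that takes the last of them takes a treated value.

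The Day 4 and Day 7 windows have the opposite gap. They stop before dosing and the following windows start the next day, so the readings taken after the second and third infusions belong to no visit.

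These readings matter to Part C. Part B was closed over the frequency and severity of adverse events after dosing (protocol 4.2), and the same section says the orthostatic series was added to learn more about the period directly after each dose. A by-arm summary that uses one post-dose set as the baseline and leaves out the others does not serve that purpose. If KAN-101 lowers pressure for some hours, the baseline error would also make later changes look more favourable on KAN-101 than they are.

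**Working it through.** The plan states no figure to reproduce on this point. The check applies the Table 4 windows literally to the planned readings.

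**Inputs.** Times per dosing day: pre-dose, 45 min, 2 h, 4 h, which is 4 (protocol 8.3.2). Dosing days: 1, 4 and 7, which is 3 (protocol 1.3.3). Positions per set: supine, standing 1 min, standing 3 min, which is 3 (protocol 8.3.2). Windows: SAP Part C Table 4. The participant is assumed to receive all three doses and to be observed for 4 hours.

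**Counts.** Sets per participant: 4 × 3 = 12, or 12 × 3 = 36 positional readings. Pre-dose sets: 1 × 3 = 3. Post-dose sets: 3 × 3 = 9.

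**Assignment.**

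| Day | Pre-dose set | Three post-dose sets |
|---|---|---|
| 1 | Baseline window, not selected | Baseline window; the 4 h set is selected as baseline |
| 4 | Day 4 | No window (the next opens on Day 5) |
| 7 | Day 7 | No window (the next opens on Day 8) |

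The baseline row's own wording selects the last Day 1 set. The tie rule points the same way, because all four Day 1 sets are equally close to Day 1 and the later value wins.

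Of the 9 post-dose sets, 1 becomes baseline, 2 (Day 1 at 45 min and 2 h) lose to it, and 6 (3 on each of Days 4 and 7) enter no window. Sets summarised as post-dose results: 9 − 1 − 2 − 6 = 0.

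**Effect on change from baseline.** Let d be the amount in mmHg by which KAN-101 lowers a pressure at the last Day 1 reading, relative to placebo. Then:

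reported change = later value − (pre-dose value − d) = true change + d

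For placebo d = 0 by definition, so the between-arm difference in change moves by +d. The documents give no value for d. Purely as an illustration, d = 0, 2, 5 or 10 mmHg gives a shift of 0, +2, +5 or +10 mmHg.

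**Reach.** Later Table 4 visits with scheduled orthostatic readings are Day 4 pre-dose and Day 7 pre-dose, so two visits are affected.

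**After correction.** With baseline limited to readings before the first dose, the Day 1 set taken about 5 minutes pre-dose is selected. With post-dose timepoints added for the three dosing days, all 9 post-dose sets have a place.

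**The case against.** The strongest reply is that this is loose drafting with little consequence. The other dosing-day rows of Table 4 are pre-dose, so a pre-dose Day 1 baseline is probably what was meant. The same baseline wording is used for vital signs in the Part A and Part B SAPs, which suggests carried-over text. Orthostatic hypotension is judged within a single supine-to-standing session (protocol 8.3.2) and recorded as an adverse event, so it reaches the adverse event tables whatever the baseline. All observations stay in the listings, and the safety board reviews unblinded safety data. Sponsor standards might already impose a pre-dose baseline. What is affected is descriptive, with no test or decision attached.

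Most of that is correct and limits the impact. It does not change what the written rule selects, and neither document says that sponsor standards override it. Listings do not compare arms, and adverse events show threshold crossings but not smaller shifts. Reading Table 4 as covering seated readings only does not help, because the orthostatic sets would then have no window at all.

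A reader might infer more than the documents support:

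- *Intent from Table 6.* Its immunogenicity baseline reads "Last observation prior to first dosing date", which looks like proof that the SAP states a pre-dose limit when it wants one. Read equally literally, that wording would exclude the Day 1 pre-dose antibody sample, the only scheduled pre-treatment one. The contrast is not reliable evidence.
- *Seated readings at all 8 later visits.* Protocol 8.3.2 states: "Vital signs will be monitored during and after study intervention infusions to assess for IRR". However, no post-infusion seated timepoints are scheduled, and nothing shows that such readings enter the database.
- *Laboratory baselines in general.* Table 5 shares the wording, but scheduled Day 1 samples are drawn pre-dose. Only an event-triggered Day 1 sample could displace them.
- *Grade 3 assignment and the date-based definition of treatment-emergent events.* The grading rule applies equally to blinded arms and no bias is shown. Reclassifying events by reading time would need links between events and readings that the documents do not describe.

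**Conclusion.** The point holds for the Part C orthostatic readings. Table 4 as written selects a post-dose baseline (about 4 hours after the first infusion on the planned schedule) and gives no window to the 6 scheduled post-dose sets of Days 4 and 7. None of the 9 post-dose sets per participant is summarised as a post-dose result. These counts assume all three doses and 4 hours of observation; a longer stay adds post-dose sets and moves the baseline later.

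The baseline error affects two comparisons, Day 4 and Day 7 pre-dose. Its size equals any drug effect remaining at the last Day 1 reading, which is unknown and may be zero. The loss of the post-dose summaries does not depend on that value. The primary endpoint, adverse event capture, listings and safety board review are untouched. This is an incorrect stated rule for a descriptive safety summary and should be corrected. It is not evidence that a safety signal has been missed.

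**What to change.** Change SAP Part C only:

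1. In Table 4, define baseline as the last observation before the start of the first infusion. Make the same edit in Table 5 for consistency; there it matters only for event-triggered Day 1 samples.
2. In Table 4 and 6.6.3, add post-dose timepoints at 45 minutes, 2 hours and 4 hours for Days 1, 4 and 7, and exempt them from the one-value-per-window rule. Summarise them by arm against the pre-dose value, including the standing-minus-supine change at 1 and 3 minutes.

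The cost is SAP wording and a few additional descriptive tables from measurements already scheduled. If sponsor standards already use a pre-dose baseline and nominal timepoints, the edit simply records that.

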In amendment 3 of this protocol, Part C is added. In Part C, the screening GC requirement is removed. As a result, the primary objective will now be evaluating the change in magnitude of IL-2 response before and after GC in KAN-101 treated versus placebo participants on Day 15. Furthermore, in order to get more insight into the events immediately subsequent to dosing, additional assessments including orthostatic vital signs, temperature, and RR are collected. Additionally, safety labs (hematology and chemistry) will be collected in case of orthostatic hypotension, syncope, or TEAE, Grade 3 or greater.

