8.3.2.1. Oral Temperature and Respiratory Rate

For Parts A and B, oral temperature and respiratory rate will be assessed. Temperature and respiratory rate findings collected during the study will be considered source data and will not be required to be reported, unless otherwise noted.

For Part C, oral temperature and RR will be assessed and recorded in clinical database at timepoints described in the [SoA](#), ie,

- Approximately 5 minutes pre-dose;
- Approximately 45 minutes, 2 hours, and then, every 2 hours until discharge from the unit post dose.

Additionally, if a participant experiences treatment-emergent, clinically significant orthostatic hypotension or syncope, then, in addition to supportive care, temperature and RR will be collected every 2 hours, until discharge. **Note:** if planned assessments (pre-dose and 45 min, 2 hr and 4 hour post-dose) overlap unplanned assessments, temperature and RR will be measured only once, not twice at that time.

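### Part C: the SAP's vital-sign windows have no post-dose row, so a windowed summary by arm would show none of the readings added to study events after infusion

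*SAP*

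**What the plan says.** **Purpose and collection.** Protocol Section 4.2 explains the Part C additions: "in order to get more insight into the events immediately subsequent to dosing, additional assessments including orthostatic vital signs, temperature, and RR are collected". The Part C SAP, Section 3.5.3, repeats the schedule around each infusion: "orthostatic vital signs including SBP, DBP, and PR will be collected approximately 5 minutes pre-dose, and approximately 45 minutes, 2 hours". After that, readings repeat at 2-hour intervals while the participant stays on site. Protocol Section 8.3.2 names 45 minutes, 2 hours and 4 hours as the planned post-dose times. Each set is read supine and after 1 and 3 minutes standing. For Part C, protocol Section 8.3.2.1 adds that "oral temperature and RR will be assessed and recorded in clinical database" at the same times.

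**Analysis.** Part C SAP Appendix 2.1 states: "Analysis windows will be used for PROs and vital signs, and laboratory tests". It makes no exception for orthostatic or post-dose readings, and it keeps one value per window (the one closest to the target day). The relevant Table 4 rows are:

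- Baseline: the last observation on or before the calendar date of first dosing
- Day 4: "Day 2 - Day 4 pre-dosing"
- Day 7: "Day 5 - Day 7 pre-dosing"
- Day 15: "Day 8 - Day 15 pre-GC"

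Section 6.6.3 is the only description of the summary: "Vital signs and change from baseline and clinical significant change will be summarized", following the sponsor's standards. Section 6 says data are summarized by treatment group.

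**The concern.** These measurements were added for a stated safety reason after Part B was closed over the frequency and severity of adverse events following dosing. Their value lies in the hours after each infusion. Table 4 has rows only for values taken before dosing or before a gluten challenge, apart from the Week 52 row and a Day 1 baseline row that does not separate pre-dose from post-dose.

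Two things follow if the table is applied as written. The by-arm vital-sign summary leaves out the period the measurements were meant to cover. The change-from-baseline columns may also be computed from a Day 1 value taken after the first infusion. In addition, an orthostatic fall is a supine-to-standing difference within one assessment. A change from study baseline at a visit does not measure it, and the SAP defines no such variable.

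**Working it through.** There is no plan figure to reproduce. The check assigns each planned reading to the Table 4 windows.

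**Inputs.** Dosing days 1, 4 and 7 (protocol Section 1.3.3). Planned times pre-dose, 45 minutes, 2 hours and 4 hours (protocol Section 8.3.2). Windows from Part C SAP Table 4. Planned size 104 (protocol Section 9.5).

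| Dosing day | Pre-dose | 45 min | 2 h | 4 h |
|---|---|---|---|---|
| Day 1 | baseline candidate | baseline candidate | baseline candidate | baseline candidate |
| Day 4 | Day 4 window | none | none | none |
| Day 7 | Day 7 window | none | none | none |

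The Day 4 post-dose readings come after the Day 4 window closes and before the next opens on Day 5. The Day 7 post-dose readings come after the Day 7 window closes and before the next opens on Day 8.

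**Counts per participant.**
- Planned post-dose timepoints: 3 times × 3 days = 9.
- In no window: 3 × 2 days = 6.
- Absorbed into baseline: 3 × 1 day = 3.
- Shown as post-dose values: 9 − 6 − 3 = 0.

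**Planned maximum over Part C.** 6 × 104 = 624 sets in no window and 3 × 104 = 312 sets inside the baseline window, together 936 = 9 × 104. This assumes that all 104 participants receive all three doses with complete readings.

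**Effect on baseline.** Let *b* be the Day 1 pre-dose value and suppose the last Day 1 post-dose reading is lower by *d*. If that reading is taken as baseline, a later value *v* gives a computed change of *v* − (*b* − *d*) = (*v* − *b*) + *d*. Every later change for that participant is shifted by *d*. If the mean of *d* differs between arms, the difference between arms in change from baseline is shifted by that difference. Table 4 also does not say which posture supplies the value.

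**Same appendix, other table.** Table 6 (immunogenicity) sets its baseline target before dosing on Day 1, so the appendix draws this distinction elsewhere. The Part C Table 4 rows match those of the Part B SAP, and Part B scheduled no orthostatic series. The likely explanation is that the table was carried over without a dosing-day section.

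**The case against.** Four points deserve weight.

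1. **Adverse events.** Protocol Section 8.3.2 defines clinically significant orthostatic hypotension by measured falls (systolic over 20 mmHg or diastolic over 10 mmHg within 3 minutes of standing) and requires a Grade 3 adverse event to be documented. Part C SAP Section 6.6.1 tabulates treatment-emergent events by preferred term and severity. A reader might infer from Table 4 that the by-arm output cannot show post-dose hypotension at all. The documents do not support that, because falls over the threshold should appear there. This point stands. The event table does not give the size of the fall, its time after infusion or falls below the threshold, and it depends on each reading being converted into an event.

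2. **Sponsor standards.** Section 6.6.3 also promises a summary of clinically significant change. The standards are not in the documents, so a reader who concludes that the readings will never be tabulated goes too far. Equally, nothing in the SAP says that this summary uses readings outside the windows or a supine-to-standing difference.

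3. **Scope of Table 4.** The protocol's schedule of activities lists ordinary vital signs and the orthostatic series on separate rows, so Table 4 may have been meant for the first only. But SAP Section 3.5.3 puts both under one heading, and Appendix 2.1 exempts neither. If Table 4 does not govern the orthostatic series, the SAP specifies no timepoints or reference value for it, and the gap remains.

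4. **No stated comparison.** A reader might infer that a planned randomized or dose-response comparison of orthostatic change is lost. Neither document names such an endpoint or question. Safety oversight does not depend on Table 4 either: Grade 3 or higher treatment-emergent events go to the DSMB, which reviews unblinded data, and all observations remain in the listings.

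**Conclusion.** The gap is real and more than missing detail. Applied as written, the windows and baseline rule leave 6 of the 9 planned post-dose timepoints unassigned and place the other 3 inside baseline, so a windowed summary by arm shows none of them as post-dose values. What is not specified by arm is the size and time course of the blood pressure and pulse change, sub-threshold falls, and temperature and respiratory rate, which the Part C SAP does not name.

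This rests on two assumptions: that Table 4 applies to the dosing-day series, and that the sponsor's standards, which cannot be seen, do not already supply a dosing-day table. The baseline distortion is possible, not certain; it occurs only where a Day 1 post-dose reading is the one selected. The totals of 624 and 936 are planned maxima, not counts of lost data: the SAP records that the study was terminated, and the number actually dosed is not given. The point concerns descriptive safety reporting and leaves the primary IL-2 analysis untouched.

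**What to change.** **Appendix 2.1.** Define the vital-sign baseline as the last value before the first dose, and state the posture used. Add a dosing-day table with nominal timepoints (pre-dose, 45 minutes, 2 hours and 4 hours on Days 1, 4 and 7), taking the same-day pre-dose set as reference.

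**Section 6.6.3.** Summarize by arm, dosing day and timepoint:
- the supine-to-standing change in systolic and diastolic pressure and pulse;
- the number and percent of participants meeting the protocol Section 8.3.2 definition, as a cross-check on the adverse event table;
- the change in temperature and respiratory rate.

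**Cost.** SAP text and one set of descriptive tables. The protocol already requires the measurements, so there is no new collection, no hypothesis test and no change to clinical procedures.
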